## 1. Study Objectives

To compare complications of contemporary treatments for prostate cancer and quality of life outcomes in men with newly diagnosed low- and intermediate-risk prostate cancer through a prospective, population-based cohort study design.

### 1.1. Objectives

To measure the self-reported, overall and disease specific health related quality of life (HRQOL) prior to treatment, at 8 months, and 12 months following active surveillance (AS), SBRT, IMRT, PGA, and RP.

To define and compare the rate of adverse events following stereotactic body radiation therapy (SBRT), partial gland ablation (PGA), intensity modulated radiation therapy (IMRT) and radical prostatectomy (RP) among men recently diagnosed with low and intermediate risk prostate cancer.

### 1.2 Hypotheses / Research Questions

PGA is associated with less reduction of urinary and sexual function compared to before treatment than both RP and IMRT. SBRT is associated with less reduction of urinary and sexual

function before treatment compared to RP and IMRT. SBRT will be associated with less reduction in bowel function compared to IMRT. PGA is associated with better overall quality of life at 12 months compared to AS.

PGA and SBRT are associated with fewer adverse events compared to RP and IMRT.

## **2. Background and Significance**

Prostate cancer remains the most commonly diagnosed, solid organ tumor and the second most common cause of cancer death in U.S. men. Technological advances have enabled new treatment options, such as stereotactic body radiation therapy (SBRT) and partial gland ablation (PGA). Although heavily marketed as more convenient with fewer side effects, there is an absence of high-level, comparative effective research (CER) to discern relative outcomes to traditional therapies such as active surveillance (AS), radical prostatectomy (RP) and intensity modulated radiation therapy (IMRT).

We will conduct a pragmatic, population-based cohort study of men with newly diagnosed low and intermediate risk prostate cancer in Southern California (SCa) and New York State (NYS) Surveillance Epidemiology and End Results (SEER) regions to bridge the evidence gap concerning adverse events and patient reported outcomes. Our proposed study will inform multiple stakeholders, who contributed to our study design. This includes prostate cancer survivors, payers, medical device manufacturers, professional organizations, community and academic prostate cancer experts and the Food and Drug Administration (FDA).

## **3. Study Design and Methods**

### **3.1 Overall Design**

We will conduct rapid case ascertainment (within 3 weeks of diagnosis or sooner) at hospitals within these National Cancer Institute-sponsored Surveillance Epidemiology and End Results (SEER) Regions where PGA and SBRT are more likely to be offered. Cases will be identified through the SEER registries' rapid case ascertainment system, and patients will be enrolled to the cohort study directly by the investigator team (not through the individual hospitals). At the time of rapid case ascertainment, the type of treatment a man receives is not yet known; therefore, we will enroll all patients diagnosed with low and intermediate-risk prostate cancer.

### **3.2 Patient Questionnaires – Refer to Appendix A.**

#### **A. Administration**

- **Timing and Frequency** – Baseline questionnaires will be sent to eligible participants for study enrollment. Follow-up questionnaires at 8 months and 12 months will be sent to enrolled participants to ascertain treatment choice and obtain patient-reported outcomes following treatment.
- **Survey method**  
Eligible participants will be mailed a survey packet consisting of a paper copy of the survey, an introductory letter and information sheet, and a postage paid return envelope. In the letter the participant will be informed that, if he wishes, he may also complete the survey online and will be given a code and link to the online survey. All materials will be provided in Spanish and English to those participants with Spanish surnames. Interviewers contacting the men are bilingual.

A modified Dillman method will be used to increase response. This includes follow-up with telephone, mail, and offers of completion of the survey online or by telephone.

Specifically, if no response is received after 2 weeks, the study staff will telephone the participant to determine if he has any questions or concerns and to encourage him to complete the survey. At least 5 calls will be made on different days, times of the day (including evenings), and on weekends to reach the person. Additional follow-up efforts will include sending reminder postcards, re-mailing of the survey packet, sending a reminder letter with the link to the online survey, or offering to do the interview over the telephone.

- **Person Identifiers**

Patient identifiers obtained at the time of rapid case ascertainment will be used to link to the completed registry abstract. The registry variables to be linked to the cases will include: patient demographic data (age, date of birth, race, socio-economic status, quintile of census block of residence, marital status, birthplace), tumor data (PSA, stage, histology, grade, clinical and pathologic Gleason score, extension), treatment data (surgical code, radiation (type), dates of treatments, chemotherapy, and hormone therapy, PGA and AS).

B. Study Instruments – Refer to [Appendix A](#).

#### **4. Study Enrollment**

##### **4.1 Study Population**

Subjects with a diagnosis of prostate cancer who meet the inclusion and exclusion criteria will be eligible for participation in this study.

##### **4.2 Inclusion Criteria**

To be included in the study, the participant will: (1) have pathologically-confirmed clinically localized prostate adenocarcinoma with Grade Group 1-2 (Gleason score 6 & 7) at one of the selected hospitals in SCa and NYS; (2) have a diagnosis date during the 18 month recruitment window; (3) speak either English or Spanish and; 4) agree to participate by completing the baseline questionnaire.

##### **4.3 Exclusion Criteria**

Patients will be **excluded** if they: 1) have clinically metastatic disease or high-risk PCa (T3a-T4, Gleason Grade Group 4 or 5 or PSA >20 ng/mL; (2) do not speak English or Spanish; or (3) are unwilling or unable (low literacy, too ill, etc.) to give informed consent; or (4) are diagnosed with prostate cancer incidentally at the time of radical cysto-prostatectomy to treat bladder cancer.

##### **4.4 Recruitment and Retention**

We will conduct rapid case ascertainment (within usually 4 weeks of diagnosis or sooner) at hospitals within these SEER Regions where PGA and SBRT are more likely to be offered in order to maximize the sample size of men receiving these new treatments.

The SCa and NYS SEER registries are mandated by their respective states to routinely collect and report information on all cancers diagnosed in their catchment areas, including sociodemographic information and tumor characteristics, such as final pathologic stage and histologic grade. Active and passive follow-up is also conducted to ascertain vital status and underlying cause of death.

The Study Advisory Committee (SAC) is comprised of patient partners Fans for the Cure and Us TOO, a senior FDA officer, and a representative from Centers for Medicare and Medicaid Services. Patient partners will participate actively in research decision-making through monthly SAC meetings. Patient partners will co-lead to troubleshoot challenges that may arise in subject recruitment, review preliminary outcomes, troubleshoot research obstacles and participate in dissemination of study findings. Patient partners will resolve potentially confusing and/or missing survey responses.

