## 1. Protocol Summary

Full Title:	Prostate Cancer Comparative Outcomes of New Conceptual Paradigms for Treatment
Short Title:	PC CONCEPT
Principal Investigators:	[name] MPH; [name] MPH
Study Description:	This study will use a population-based cohort design to study men with newly diagnosed low- and intermediate-risk prostate cancer at high-volume centers in Southern California (SCa) and New York State (NYS). Complications of contemporary treatments for prostate cancer and quality of life outcomes, such as general health, urinary, sexual, and bowel function, cancer anxiety, and treatment regret will be compared and tracked over the course of this study.
Sample Size:	N= 3,657
Enrollment:	This study will enroll 2,378 subjects and screen up to 3,657 subjects.
Study Population:	Subjects will have pathologically-confirmed clinically localized prostate adenocarcinoma with National Comprehensive Cancer Network (NCCN) low (T1-T2a, Gleason 6, Grade Group 1, PSA <10 ng/mL) or intermediate risk (T2b-T2c or, Gleason 7, Grade Group 2 or 3 or PSA 10-20 ng/mL) at one of the selected hospitals in SCa and NYS. Subjects must also have a diagnosis date during the 18-month recruitment window.
Enrollment Period:	18 months
Study Design:	Prospective, observational
Description of Sites	Patient enrollment at 15 sites within SCa and NYS, identified through National Cancer Institute-sponsored Surveillance Epidemiology and End Results (SEER)
Study Duration:	01Oct2020 - 30Nov2023
Participant Duration:	12 months
Primary Objectives:	To measure the self-reported, overall and disease specific health related quality of life (HRQOL) prior to treatment, at 8 months, and 12 months following active surveillance (AS), SBRT, IMRT, PGA, and RP.

To define and compare the rate of adverse events following stereotactic body radiation therapy (SBRT), partial gland ablation (PGA), intensity modulated radiation therapy (IMRT) and radical prostatectomy (RP) among men recently diagnosed with low and intermediate risk prostate cancer.

Primary Endpoints:	Change from Baseline in Patient-Reported Quality of Life as Measured on EQ-5D-5L at 8 Months & 12 Months following Treatment
	Change from Baseline in Patient-Reported Urinary, Sexual, and Bowel Function as Measured on EPIC-26 at 8 Months & 12 Months following Treatment

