## 7. Data Reporting / Regulatory Considerations

The SCa and NYS SEER research teams will independently contact participants, collect data and enter survey results in a unified study database maintained at USC. A Study ID will be created for each case and survey and registry data will be linked to it, and no personal identifiers (or registry IDs) will be included in the analytic dataset. Only staff directly involved with the study at each site will have access to the tracking systems. In addition, a central database will be maintained at Weill Cornell to assess the overall progress of the project. Each site will maintain a local password-protected and secure linkage database containing participant protected health information and identifiers and the linkage to the Study ID number. This database will only be accessible to researchers at the local site where the participant is followed. Participants will return their questionnaires to the local investigators. Accordingly, local study staff will go over each completed questionnaire and check all coding (although the questionnaire will be designed to be self-coded when possible).

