For adverse events, we expect a rate of 10% in the IMRT and RP arms. The main HRQOL endpoint of interest is EPIC-26 sexual function. The estimated number of patients we will evaluate is as follows: AS 300; PGA: 280; SBRT: 288; IMRT: 316; RP: 333. This is based on the incidence of low and intermediate prostate cancer in the SCa and NYS SEER registries.

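### Section 4.4 tells patient partners to resolve unclear or missing survey answers, without defining the task or requiring that the respondent be asked

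*Combined protocol and SAP*

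**What the plan says.** Section 4.4 (Recruitment and Retention) describes the advisory structure: "The Study Advisory Committee (SAC) is comprised of patient partners", together with agency representatives. The partners are two named organisations. Their duties include this one: "Patient partners will co-lead to troubleshoot challenges that may arise in subject recruitment, review preliminary outcomes, troubleshoot research obstacles". The paragraph then closes with: "Patient partners will resolve potentially confusing and/or missing survey responses". No qualification follows, and no other section returns to this task.

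Other sections give the handling of questionnaires to other people. Section 3.2 has study staff telephone and re-mail men who have not replied. Section 7 has the SEER research teams contact participants, collect data and enter results, and adds that "local study staff will go over each completed questionnaire and check all coding".

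The surveys carry most of the primary endpoints in the Protocol Summary, for example "Change from Baseline in Patient-Reported Urinary, Sexual, and Bowel Function as Measured on EPIC-26 at 8 Months & 12 Months following Treatment" and "Change from Baseline in Patient-Reported Quality of Life as Measured on EQ-5D-5L at 8 Months & 12 Months following Treatment". Section 8 states: "The main HRQOL endpoint of interest is EPIC-26 sexual function".

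**The concern.** A patient-reported outcome has its standing because the answer comes from the patient. If someone else decides what an unclear answer meant, or what a blank would have been, the value is that person's judgement recorded under the patient's name. The sentence in Section 4.4 gives that task to people who are neither respondents nor described as data staff, and it sets no limits.

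Two things are at stake. The first is the validity of the questionnaire scores on which the treatment comparisons rest. The second is visibility: a filled blank no longer counts as missing, so neither the analyst nor a reader could see how much of a score was the respondent's own.

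**Working it through.** No arithmetic applies, because the plan states no figure on this point. The check sets the sections side by side.

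1. **What the verb acts on.** In Section 4.4 the object is survey responses, including missing ones. It is not survey questions or response rates. A missing response can be dealt with in three ways: ask the man, supply a value without him, or leave it missing. The sentence does not choose among them. General help with obstacles is already covered by the preceding sentence in 4.4, so this one appears to add something more.

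2. **Who else holds the task.**
   - Following up men who have not returned a survey: study staff (Section 3.2).
   - Contact, collection and data entry: SEER research teams (Section 7).
   - Review of each completed form and its coding: local study staff (Section 7).
   - Unclear or missing responses: patient partners (Section 4.4).

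   The last item overlaps with the other three. No section says how the work passes between them or who has the final say. Section 3.2 covers surveys that are not returned, and it does not cover items skipped on a returned survey.

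3. **Which endpoints are reached.** The Protocol Summary lists seven primary endpoints. Five are questionnaire scores: EQ-5D-5L, EPIC-26, MSHQ-EjD, MAX-PC and treatment regret. The other two are adverse events and recurrence. The summary ties these to CTCAE and medical records, but the schedule in Section 6.1 also lists both under patient-reported elements.

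4. **Treatment classification.** Section 3.2 says that the follow-up questionnaires also serve to establish which treatment the man chose. The grids in both follow-up surveys in Appendix A let him tick several treatments, so ambiguous answers are foreseeable. The registry also supplies treatment data (Sections 3.2 and 6.1), which limits the exposure, but the plan does not say which source prevails when they differ.

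5. **What happens downstream.** Section 8 fits a GEE model to the patient-reported scores, with treatment indicators and the baseline disease-specific score as covariates. It recognises missing time points. It gives no rule for missing items and does not mention resolved values. No section asks for a flag or an audit trail. A value settled by a partner would therefore be analysed as a self-report, whether it fell in an outcome, in the baseline score or in the treatment indicator.

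6. **Size.** A bias estimate would need the share of items affected, the difference in how they were settled between treatment groups, and the link from item to domain score. The documents give none of these.

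**The case against.** The strongest reply is that the sentence means advice. It closes a paragraph on committee duties, under a recruitment heading, and does not stand in the data-handling or statistical sections. The operational work is assigned to staff elsewhere. Unclear responses might also mean free-text entries, which are not scored items. This may well be what the sponsor intended. It stands as a reason not to allege a procedure of altering data. It does not cure the text, which names responses, includes missing ones, and says they will be resolved.

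A reader might infer more than the documents support:

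- **That partners edit or enter data.** No section says so or gives them access to records. The literal text permits it but does not describe it.
- **That partners know a man's treatment, or results by group.** Section 4.4 says that they see preliminary outcomes. It does not say that these are split by treatment, or that partners see any individual's treatment. The follow-up forms do list treatments received, but local staff who check them see that too.
- **That the access rules in Section 7 contradict Section 4.4.** The restriction to local-site researchers covers the local linkage file of identifiers and health information. It does not govern the survey answers in the unified database. The conflict is one of overlapping roles.
- **That a shift of a given number of points follows.** Any such figure would rest on invented inputs.

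**Conclusion.** The point holds in a limited form. Section 4.4 grants an undefined authority over individual survey responses to people other than the respondent. It overlaps with the staff roles in Sections 3.2 and 7, and it contains no requirement to go back to the participant. Followed as written, the rule could put values that are not self-reported into five of the seven primary endpoints and into the treatment classification, and Section 8 would not distinguish them.

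The conclusion rests on the literal wording and on the absence of any definition elsewhere. It does not assume that partners have altered or would alter answers, and it does not depend on what they know about treatment. The direction and size of any bias cannot be derived from the documents. The case for the change is that an instruction touching the primary outcomes is open to a harmful reading and can be closed at little cost.

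**What to change.** Replace the sentence in Section 4.4 with text to this effect: patient partners advise on survey wording and on general patterns of non-response or confusion only; individual answers are clarified or completed only by the participant himself, when queried by local study staff; items still unanswered stay missing and follow the scoring rules of the instrument.

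This keeps a real role for the partners and brings Section 4.4 into line with Sections 3.2 and 7. If advice was all that was meant, the edit only makes the text say so.

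The cost is a short protocol amendment, which needs ethics approval under Section 7.1, and slightly more item-level missing data than if blanks were filled.

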## 6. Study Procedures

### 6.1 Schedule of Trial Events

Data elements	Baseline	8 months	12 months
Patient reported			
Income	X		
Education	X		
Family history of prostate cancer	X		
Employment status	X	X	X
Charlson co-morbidity	X	X	X
Height	X	X	X
Weight	X	X	X
Medications	X	X	X
Treatment (confirm PGA and SBRT)			
Cancer recurrence		X	X
Secondary treatment(s)		X	X
Adverse events		X	X
Patient reported outcomes	X	X	X
Registry reported			
Age	X		
Race	X		
Marital status	X		
Insurance type	X		
Poverty level based on census tract	X		
PSA	X		
Biopsy pathology	X		
Clinical stage	X		
Treatment	X		

## 7. Data Reporting / Regulatory Considerations

The SCa and NYS SEER research teams will independently contact participants, collect data and enter survey results in a unified study database maintained at USC. A Study ID will be created for each case and survey and registry data will be linked to it, and no personal identifiers (or registry IDs) will be included in the analytic dataset. Only staff directly involved with the study at each site will have access to the tracking systems. In addition, a central database will be maintained at Weill Cornell to assess the overall progress of the project. Each site will maintain a local password-protected and secure linkage database containing participant protected health information and identifiers and the linkage to the Study ID number. This database will only be accessible to researchers at the local site where the participant is followed. Participants will return their questionnaires to the local investigators. Accordingly, local study staff will go over each completed questionnaire and check all coding (although the questionnaire will be designed to be self-coded when possible).

## **7.1 Institutional Review Board/Ethics Committee Approval**

As required by local regulations, the Investigator will ensure all legal aspects are covered, and approval of the appropriate regulatory bodies obtained, before study initiation.

Before initiation of the study at each study center, the protocol, the ICF, other written material given to the patients, and any other relevant study documentation will be submitted to the appropriate Ethics Committee. Written approval of the study and all relevant study information must be obtained before the study center can be initiated. Any necessary extensions or renewals of IEC/IRB approval must be obtained for changes to the study, such as amendments to the protocol, the ICF, or other study documentation. The written approval of the IEC/IRB together with the approved ICF must be filed in the study files.

The Investigator will report promptly to the IEC/IRB any new information that may adversely affect the safety of the subjects or the conduct of the study. The Investigator will submit written summaries of the study status to the IEC/IRB as required. On completion of the study, the IEC/IRB will be notified that the study has ended.

All agreed protocol amendments will be clearly recorded on a protocol amendment form and will be signed and dated by the original protocol approving signatories. All protocol amendments will be submitted to the relevant institutional IEC/IRB for approval before implementation, as required by local regulations. The only exception will be when the amendment is necessary to eliminate an immediate hazard to the trial participants. In this case, the necessary action will be taken first, with the relevant protocol amendment following shortly thereafter.

Once protocol amendments or consent form modifications are implemented at the lead site, Weill Cornell Medicine, updated documents will be provided to participating sites. Weill Cornell Medicine must approve all consent form changes prior to local IRB submission.

Relevant study documentation will be submitted to the regulatory authorities of the participating countries, according to local/national requirements, for review and approval before the beginning of the study. On completion of the study, the regulatory authorities will be notified that the study has ended.

## **7.2. Ethical Conduct of the Study**

The Investigators and all parties involved should conduct this study in adherence to the ethical principles based on the Declaration of Helsinki, GCP, ICH guidelines and the applicable national and local laws and regulatory requirements.

This study will be conducted under a protocol reviewed and approved by the applicable ethics committees and investigations will be undertaken by scientifically and medically qualified persons, where the benefits of the study are in proportion to the risks.

